7.8.2 Laboratory data

The analyses of laboratory data will be descriptive in nature and will be based on BI standards “Display and Analysis of Laboratory Data” (7). CTC grade for applicable lab parameters will be calculated according to CTCAE v5.0 (6).

Descriptive statistics of all converted laboratory values by visit will be provided including changes from baseline. Frequency tables of transitions relative to the reference range and of possible clinically significant abnormalities will be produced. For those parameters that have CTC grading possible clinically significant abnormalities are defined as those laboratory values with a CTC grade ≥ 2 that have had an increase of ≥ 1 grade from baseline. For those parameters for which no CTC grade has been defined standard BI project definitions will be used to decide on clinical significance. Further frequency table will show the transition of CTC grade from baseline to worst value and from baseline to last value on treatment.

Summaries will be produced of laboratory data recorded prior to treatment, on-treatment and post-treatment. For details on the treatment definition, see [Section 6.1](#).

The focus of the laboratory data analysis will be on the following laboratory parameters:

[figure not shown]
- Low values: Activated Partial Thromboplastin Time (aPTT), Prothrombin Time (PT), International Normalised Ratio (INR), White Blood Cell Count (WBC) with differential, Platelets (PLT)
- High values: Aspartate Aminotransferase (AST), Alanine Aminotransferase (ALT), bilirubin, Alkaline Phosphatase (AP), Activated Partial Thromboplastin Time (aPTT), Prothrombin Time (PT), International Normalised Ratio (INR), Protein levels in urine

7.8.3 Vital signs

Only descriptive statistics are planned for this section of the report. A shift table will be provided for change from baseline over the course of treatment for systolic and diastolic blood pressure.

7.8.4 ECG

ECG data will be collected as described in CTP Section 5.2.4. Clinically significant findings in ECG data will be reported under “Adverse events” if applicable and will be analysed accordingly. In addition, patients with abnormal overall assessments at any time on treatment will be summarized in a descriptive manner.

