6.7 BASELINE, TIME WINDOWS AND CALCULATED VISITS

Visit labels

Study days and visits will be labelled according to the flow charts in the CTP. The visit schedule with accompanying details can also be found in the flow charts in the CTP.

Definition of “baseline”

For laboratory values, the baseline value is the most recently observed value before or on the first day of infusion of trial medication; for laboratory measurements, the examination time may also need to be considered, in instances where time is recorded in addition to date. For all other data values, baseline is defined as the most recent measurement taken prior to first administration of trial medication. If not available, then the values reported at the screening visit will be considered.

Time windows

Time windows and visits will be calculated to determine the planned day of tumour measurement and response status based on the protocol-specified tumour imaging schedule. Imaging data will be displayed as: Screening, Week 6, Week 12, Week 18, etc. The number of weeks will be calculated using their relative day (from start of treatment) using a ±3 week window. (Images taken in the first 3 weeks from start of treatment will be assigned to Week 6.) Images which are not older than 28 days at start of treatment will be sufficient as screening images and do not need to be repeated.

How to include measurements taken between time windows

The same visit windows will be used for safety laboratory and vital sign assessments. If there are multiple safety or laboratory values in one time window on treatment, the worst value will be selected for the by-visit analyses.

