7.8 SAFETY ANALYSIS

The safety analyses will be performed as defined in the CTP. All safety analyses will be performed on the treated set of Part 1 and Part 2 of this trial.

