7.8.1 Adverse events

The analyses of adverse events (AE) will be descriptive in nature. All analyses of AEs will be based on the number of patients with AEs and not on the number of AEs. Two analyses will be performed. The first analysis of safety will be performed for the first part of the trial (determination of the MTD/RP2D, first cycle only, dose level = initial dose at the start of the treatment, treated set). This descriptive analysis will evaluate the MTD/RP2D. The second analysis will be performed with respect to all cycles for part 1 and will act as a support for the determination of the MTD/RP2D (treated set).

For analysis of duration, severity, etc. of multiple AE occurrences, data on the case report form (CRF) will be collapsed into AE episodes provided that all of the following applies:

- The same MedDRA lowest level term was reported for the occurrences.
- The occurrences were time-overlapping or time-adjacent (time-adjacency of two occurrences is given if the second occurrence started on the same day or on the day after the end of the first occurrence).
- Treatment did not change between the onset of the occurrences or treatment changed between the onsets of the occurrences, but no deterioration was observed for the later occurrence.

For further details on summarization of AE data, please refer to the guideline 'Handling and summarization of adverse event data for clinical trial reports and integrated summaries' ([5](#)).

For patients treated with the test drug, that means that all adverse events occurring between first drug infusion and the REP after last drug infusion or death, whichever occurs first, will be assigned to the on-treatment period. All adverse events occurring before any study drug infusion will be assigned to 'screening' and all adverse events occurring after last study drug infusion + the REP will be assigned to 'post-study' (for listings only). For details on the treatment definition, see [Section 6.1](#).

An overall summary of adverse events will be presented. This summary will exclude the rows 'Severe AEs', 'Significant AEs' and 'Other significant AEs' but will include additional rows for 'AEs leading to dose reduction', 'AEs leading to death' and 'AEs by highest Common Terminology Criteria (CTC) grade'.

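### The ECG summary in SAP Section 7.8.4 does not use baseline, so it cannot separate pre-existing from newly abnormal ECGs (minor; a shift table would resolve it)

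*SAP*

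**What the plan says.** SAP Section 7.8.4 gives ECG data two routes. First, "Clinically significant findings in ECG data will be reported under" adverse events where applicable, and are analysed with them. Second, as an additional display, "patients with abnormal overall assessments at any time on treatment will be summarized in a descriptive manner". That is the only ECG-specific table the section describes. For ECG it cites the protocol on how the data are collected.

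Four other places in the SAP bear on the point:

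- **Section 6.7** sets the baseline for everything other than laboratory values: "For all other data values, baseline is defined as the most recent measurement taken prior to first administration of trial medication". ECG falls under this.
- **Section 7.8.2** plans, for laboratory data: "Further frequency table will show the transition of CTC grade from baseline to worst value and from baseline to last value on treatment". It also requires an increase of at least one CTC grade from baseline before a graded laboratory value counts as possibly clinically significant.
- **Section 7.8.3** plans, for vital signs: "A shift table will be provided for change from baseline over the course of treatment for systolic and diastolic blood pressure".
- **Section 7.8** says in general: "The safety analyses will be performed as defined in the CTP".

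**The concern.** Followed literally, the rule in 7.8.4 selects a patient on one fact: an abnormal overall assessment at some time on treatment. Two different groups meet it: patients whose ECG was already abnormal and remained so, and patients whose ECG changed after treatment began. Only the second group bears on whether the combination affects the ECG.

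This matters more than it would in a controlled trial. Section 6.1 describes an open-label, non-randomized trial, and the SAP names no control group whose rate could absorb the background. The patient's own baseline is the natural reference, and the SAP has already defined it. The SAP also treats cardiac events as worth tracking: cardiac failure, cardiomyopathy and cardiac arrhythmias are among the special search categories of Section 7.8.1. An ECG table that cannot tell old findings from new ones adds little to that assessment.

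**Working it through.** **Comparison of the text.** The SAP states no figure on this point, so there is none to reproduce. The planned displays for the three measured safety domains are:

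| Domain | SAP section | Stated comparison with baseline |
|---|---|---|
| Laboratory data | 7.8.2 | Change from baseline by visit; CTC grade transition to worst and to last value on treatment |
| Blood pressure | 7.8.3 | Shift table |
| ECG | 7.8.4 | None stated |

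The baseline definition in 6.7 applies to all three, through its laboratory rule or its rule for other data. ECG is the only one of the three whose display does not use it.

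**Illustration of the mixing.** All inputs here are assumptions; none comes from the SAP. Let

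- b = share of patients with an abnormal baseline ECG, varied from 10% to 50%;
- r = share of those who are still abnormal at some time on treatment, first set to 1 (full persistence);
- n = share of patients normal at baseline who become abnormal on treatment, set to 10%.

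Then

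- reported abnormal = b × r + (1 − b) × n
- newly abnormal = (1 − b) × n

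With r = 1 and n = 0.10:

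| b | Reported | Newly abnormal | New as share of reported |
|---|---|---|---|
| 10% | 0.10 + 0.90 × 0.10 = 19% | 9% | 9/19 = 47% |
| 20% | 0.20 + 0.80 × 0.10 = 28% | 8% | 8/28 = 29% |
| 40% | 0.40 + 0.60 × 0.10 = 46% | 6% | 6/46 = 13% |
| 50% | 0.50 + 0.50 × 0.10 = 55% | 5% | 5/55 = 9% |

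The result depends heavily on b and r. With b = 20% and r = 0.5, the reported share is 0.20 × 0.5 + 0.80 × 0.10 = 18%, of which 8 points are new (8/18 = 44%). With b = 0 the table shows only new abnormalities and there is no mixing.

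Across the rows with r = 1, the reported percentage rises while the newly abnormal percentage falls. The reported figure therefore follows the baseline prevalence more than any change on treatment. Two cohorts with the same 10% risk of a new abnormality could show very different totals only because their patients entered with different ECGs.

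**The case against.** Several arguments go the other way.

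- **The table is not called treatment-emergent.** A reader might infer that the SAP presents pre-existing abnormalities as though treatment had caused them. The text does not support that. It says only that the patients were abnormal on treatment and will be "summarized in a descriptive manner"; it does not call the findings new or worsened. The defect is that the table cannot separate the groups, not that it mislabels them.
- **Clinically significant findings go to the AE analysis, which handles timing.** This is correct: "All adverse events occurring before any study drug infusion will be assigned to" the screening period (Section 7.8.1), and special search categories cover cardiac events. But this route takes only findings judged clinically significant, and its period rule applies to AEs, not to the additional ECG table.
- **The protocol may specify more.** Section 7.8 defers to it generally and it is not at hand, so a baseline split there cannot be excluded. Nor does the sentence in 7.8.4 forbid one. Still, 7.8.4 cites the protocol for ECG collection and then states its own summary, and a programmer following that sentence would produce the undivided count.
- **Different data types may have different displays.** Laboratory values have graded scales, and hypertension is a named search category. The contrast with 7.8.2 and 7.8.3 is therefore an inconsistency of approach, not a contradiction.
- **Baseline is not the only possible reference.** Part 1 also allows a descriptive comparison across BI 836880 dose levels. That stands, although differences between dose levels in baseline ECG status would still affect it.

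**Conclusion.** The point holds as a minor one. As written, the ECG table pools persistent pre-existing abnormalities with new ones, while the SAP defines a usable baseline and applies a baseline comparison to laboratory data and blood pressure.

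The amount of mixing cannot be obtained from the SAP. The illustrative range of 19% to 55% reported, against 9% to 5% new, rests wholly on an assumed 10% to 50% abnormal at baseline, full persistence, and a 10% rate of new abnormality. Lower prevalence or less persistence would shrink it.

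A reader might also infer that the safety conclusions or dose selection are compromised. The SAP gives no ground for that: the ECG count enters neither the DLT endpoint, nor the MTD/RP2D determination, nor the objective response analysis, nor any listed secondary endpoint. The effect is limited to how one descriptive safety table can be interpreted.

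**What to change.** In Section 7.8.4, replace the count with a shift table of the overall ECG assessment:

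- rows: baseline as defined in Section 6.7 (normal, abnormal, missing);
- columns: worst on-treatment assessment, with a category for missing;
- by initial dose level in Part 1 and by cohort in Part 2, in line with the display rules of Section 6.1.

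Report the number newly abnormal among patients normal at baseline, with that group as the denominator. The total abnormal on treatment can still be read from the column margin, so nothing now planned is lost. If the sponsor prefers to keep the present layout, splitting the count by baseline status would also serve.

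One limit should be noted. If the assessment is recorded only as normal or abnormal, worsening in a patient already abnormal at baseline will not show in the table and will depend on the AE route. The recorded categories should be checked against the protocol and the eCRF before the shell is fixed.

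The cost is one sentence in the SAP and one table shell. Provided a pre-treatment ECG is recorded, as the baseline definition presupposes, no added procedure is needed.
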